### 3.0 Introduction

This Statistical Analysis Plan (SAP) describes the statistical methods that will be used during the analysis and reporting of data collected under Medicines for Malaria Venture (MMV) Protocol MMV\_OZ439\_16\_01.

This SAP should be read in conjunction with the study protocol and case report form (CRF). This version of the SAP has been developed using the protocol version 2.0 dated 16-Mar-2017 (including all amendments up to this protocol date) and the final CRF(s) dated 24-Mar-2017.

An approved and signed SAP is a requirement for database hard lock.

This SAP only covers the results that will be processed by the PRA Early Development Services (EDS) Biostatistics Department.

PRA EDS will perform the pharmacokinetic (PK) (except the exploratory endpoint), safety and tolerability evaluation. Estimation of fraction absorbed, extraction ratio, liver first pass and deconvolution of absorption profile over time for OZ439 will be performed by BEL Pharm Consulting and reported in the clinical study report (CSR). Future OZ439 metabolites analysis that may be performed will not be reported in the CSR.

This SAP supersedes the statistical considerations identified in the protocol; where considerations are substantially different, they will be so identified. Any post-hoc or unplanned analyses, or significant changes from the planned analysis in this SAP performed to provide results for inclusion in the CSR but not included in this SAP, will be clearly identified in Section 9.8.2 of the CSR. Changes to planned analyses do not require an updated SAP but should be included in the CSR if significant.

### 4.0 Changes from Previous Version of Approved SAP

This is the first version of the SAP.

### 5.0 Study Objectives

#### 5.1 Primary

- To determine the absolute bioavailability of OZ439 following a single oral dose of OZ439 dispersion and a simultaneous single intravenous (iv) microdose (100 µg) infusion of [C]-OZ439 under fasted conditions (Part 1)
- To evaluate the effects of a single oral dose of cobicistat, a strong cytochrome P450 (CYP) 3A4 inhibitor, on the PK profile of a single oral dose of a dispersion of OZ439 simple granules under fasted conditions (Part 2)
- To evaluate the PK of single doses of OZ439 granules when restricting the target dosing volumes to 64.5 or 100 mL (Parts 1 and 2)

#### 5.1.1 Primary Endpoints

- Part 1: PK: absolute oral bioavailability ( $F_{po}$ ) of OZ439
- Part 2: PK of OZ439:  $C_{max}$ ,  $C_{168h}$ ,  $AUC_{0-168h}$  and  $AUC_{0-inf}$

#### 5.2 Secondary

- To assess the safety and tolerability of OZ439 when administered alone, and to assess the safety and tolerability of OZ439 and cobicistat when co-administered as single doses to healthy subjects (Parts 1 and 2)
- To determine the PK parameters of OZ439 single iv microdose (100 µg) infusion of [C]-OZ439 (Part 1)

- To assess the effects of the total dosing volume and of dose to volume ratio on OZ439 PK under fasted conditions (Parts 1 and 2)
- To determine the PK parameters and exposures of cobicistat (Part 2)

## 5.2.1 Secondary Endpoints

### Part 1:

- PK for iv administration of OZ439:  $V_d$ , CL,  $t_{1/2}$ ,  $AUC_{0-t}$ ,  $AUC_{0-inf}$  and  $\lambda_z$
- PK for oral administration of OZ439:  $C_{max}$ ,  $t_{max}$ ,  $t_{1/2}$ ,  $C_{168h}$ ,  $AUC_{0-168h}$ ,  $AUC_{0-t}$ ,  $AUC_{0-inf}$ , CL/F and  $\lambda_z$
- Safety: adverse events (AE), clinical laboratory, vital signs, electrocardiogram (ECG) and physical examination

### Part 2:

- PK of OZ439:  $t_{max}$ ,  $t_{1/2}$ ,  $AUC_{0-t}$  and  $\lambda_z$
- PK of cobicistat:  $C_{max}$ ,  $t_{max}$ ,  $t_{1/2}$ ,  $AUC_{0-t}$ ,  $AUC_{0-inf}$ , CL/F and  $\lambda_z$
- Safety: AEs, clinical laboratory, vital signs, ECG and physical examination

## 5.2.2 Exploratory Endpoints

- Part 1: Estimation of fraction absorbed, extraction ratio, liver first pass and deconvolution of absorption profile over time for OZ439
- Future OZ439 metabolites analysis may be performed (Part 1 and Part 2)

## 6.0 Study Design

### Part 1

This is an open-label study in 8 healthy subjects to determine the absolute bioavailability of OZ439 following a single oral dose of OZ439 and a simultaneous single iv infusion of [ $^{14}C$ ]-OZ439 radiolabeled microdose administered at the anticipated  $t_{max}$  of the oral dose. Subjects will receive the following treatment:

Treatment A: a single oral dose of 800 mg OZ439 simple granules administered as a 100-mL dispersion followed by a 15-minute 10-mL iv infusion of 100  $\mu g$  [ $^{14}C$ ]-OZ439 (47 kBq [1.27  $\mu Ci$ ]) beginning 3 hours after the oral dose administration.

### Part 2

This is an open-label, randomized, single-dose, 3-way cross-over study in 18 healthy subjects. Each subject will participate in 3 treatment periods and each subject will receive a single dose of each of the following 3 treatments in a randomized order with a 14-day wash-out period between each treatment:

Treatment B: a single oral dose of 800 mg OZ439 simple granules administered as a 64.5-mL dispersion

Treatment C: a single oral dose of 400 mg OZ439 simple granules administered as a 64.5-mL dispersion

Treatment D: a single oral dose of 400 mg OZ439 simple granules administered as a 64.5-mL dispersion and co-administered with a 150 mg cobicistat tablet (CYP3A4 inhibitor)

## 6.1 Sample Size Considerations

The study is exploratory and no formal sample size calculation has been made. Based on experience from previous similar studies and taking into account OZ439 large variability, a total of 8 subjects enrolled in Part 1 of the study to achieve a minimum of 6 evaluable subjects is considered sufficient. A total of 8 subjects is also considered sufficient to assess the effects of the total dosing volume and of dose to volume ratio on OZ439 PK under fasted conditions (in combination with Part 2). In Part 2 of the study a sample size of 18 subjects is considered appropriate to estimate the increase in OZ439 exposure in the

presence of a single dose of 150 mg cobicistat with sufficient precision, assuming a mean ratio of 2. Based on the assumptions of a point estimate (mean ratio) of 2.0 and a CV of 23%, a sample size of 18 subjects would give a 90% confidence interval (CI) of 1.75 - 2.28 and this number of subjects is therefore considered sufficient. In Part 2, 18 subjects will be randomized to ensure data in 15 evaluable subjects for the PK endpoints. A subject will be considered evaluable for the primary analysis if they have sufficient PK data to estimate the primary endpoints  $C_{max}$  and  $AUC_{0-inf}$  for the 3 treatments. Note: the primary analysis refers to the statistical analysis of the treatment comparisons defined in Section 16.3.1.

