## 6.2 Randomization

Subjects who have met all eligibility criteria will receive a subject number upon inclusion in the study (for Part 1: subject numbers 101-108; for Part 2: subject numbers 201-218). They will receive the subject number according to the order of enrolment in Part 1 of the study, and according to the randomization code generated by the Biostatistics Department of PRA in Part 2 of the study. The subject number will ensure identification throughout the study. Replacement subjects will receive the number of the subject to be replaced, increased by 1000 (e.g. 1101 replacement number for subject number 101), and will be administered the same or remaining treatments in the same order.

In Part 2, subjects were randomized to 1 of 6 treatment sequences (BCD, BDC, CBD, CDB, DBC, or DCB), with 3 subjects per sequence (balanced randomization).

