### 10.4 Pharmacokinetic Summary

The PK summary set will consist of all subjects who are considered evaluable for the primary statistical analysis, defined as follows:

For Part 2, a subject will be considered evaluable for the primary statistical analysis if they have sufficient PK data to estimate the primary endpoints  $C_{max}$  and  $AUC_{0-inf}$  for the 3 treatments.

For Part 1, a subject will be considered evaluable for the primary statistical analysis (bioavailability) if they have sufficient PK data to estimate the primary endpoint  $F_{po}$ .

This set will be used for the statistical analysis of the treatment comparisons defined in Section 16.3.1.

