### Part 2:

An analysis of variance (ANOVA) will be performed on OZ439 PK parameters  $C_{max}$ ,  $C_{168h}$ ,  $AUC_{0-168}$  and  $AUC_{0-\infty}$  using the SAS procedure for mixed effect models (PROC MIXED). The PK parameters will be natural logarithm transformed prior to analysis. The model will include fixed effects for treatment, period, and sequence, and a random effect for subject within sequence (comparisons D vs C and B vs C; for comparison B vs A only a fixed effect for treatment will be included).

From the ANOVA model the back-transformed least-squares means (LSMeans) for test and reference treatments will be presented. The ratios of the LSMean for the comparison of the treatments D vs C, B vs A and B vs C will be obtained by exponentiating the difference of the LSMean on the log scale. This ratio and the corresponding 90% CI will be presented for the comparisons between:

- Treatment D vs Treatment C to assess the effect of cobicistat on OZ439
- Treatment B vs Treatment A to explore volume effect (for this no within-subject comparison is possible)
- Treatment B vs Treatment C to explore dosing solution concentration effect (Treatment C will be dose normalized to 800 mg (only for this comparison))

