## Appendix 5: List of End of Text Tables and Figures

List of End of Text Tables and Figures:		
Output	Title	Population Set
15.1 Demographic Data		
Table 15.1.1	Summary of Subject Disposition	Safety
Table 15.1.2	Summary of Demographics	Safety
Table 15.1.3	Summary of Dosing	Safety
15.2 Pharmacokinetic Data		
Table 15.2.1	Summary and Listing of OZ439 and Cobicistat Plasma Concentrations	PK
Table 15.2.2	Summary and Listing of OZ439 and Cobicistat PK Parameters	PK
Table 15.2.3	Statistical Analysis of Absolute Bioavailability (Part 1)	PK
Table 15.2.4	Statistical Analysis of OZ439 PK Parameters (Part 2)	PK
Figure 15.2.5	Mean Plot of Oral OZ439 Concentration, IV Total Radioactivity and OZ439 Radioactivity versus Time (Linear and Semi-logarithmic)	PK
Figure 15.2.6	Mean Plot of Oral Cobicistat Concentration vs Time (Linear)	PK
Figure 15.2.7	Plot of Combined Individual OZ439 and Cobicistat Plasma Concentrations versus Time (Linear and Semi-Logarithmic)	PK
Figure 15.2.8	Plot of Individual OZ439 and Cobicistat Plasma Concentrations versus Time (Linear and Semi-Logarithmic)	PK
15.3 Safety Data		
15.3.1 Adverse Events		
Table 15.3.1.1	Summary of TEAEs by System Organ Class and Preferred Term	Safety
Table 15.3.1.2	Summary of Related TEAEs by System Organ Class and Preferred Term	Safety
Table 15.3.1.3	Summary of TEAEs by Relationship and Severity	Safety
15.3.2 Lists of Deaths, Other Serious and Significant Adverse Events		
Table 15.3.2	Listing of Deaths and Other Serious Adverse Events	Safety
15.3.3 Clinical Laboratory		

Table 15.3.3.1	Listing of Abnormal Laboratory Values	Safety
Table 15.3.3.2	Summary of Clinical Laboratory Data - Clinical Chemistry	Safety
Table 15.3.3.3	Summary of Clinical Laboratory Data - Hematology	Safety
15.3.4 Other Safety Parameters		
Table 15.3.4.1	Summary of Vital Signs	Safety
Table 15.3.4.2	Summary of 12-Lead Electrocardiogram	Safety
Table 15.3.4.3	Frequency Table of QTc Values	Safety
Table 15.3.4.4	Frequency Table of QTc Change from Baseline Values	Safety

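### Does the Part 2 precision statement fail because it is worked out for 18 subjects when only 15 evaluable subjects are assured?

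*SAP*

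**What the plan says.** SAP Section 6.1 opens by describing the study as exploratory and says that no formal sample size calculation was made. For Part 2 it then gives an expected precision: "Based on the assumptions of a point estimate (mean ratio) of 2.0 and a CV of 23" per cent, "a sample size of 18 subjects would give a 90% confidence interval (CI) of 1.75 - 2.28", and it judges this number of subjects sufficient. The next sentence adds that "18 subjects will be randomized to ensure data in 15 evaluable subjects for the PK endpoints". A subject is evaluable if Cmax and AUC0-inf can be estimated for all three treatments.

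Section 10.4 defines the set for the comparisons: "The PK summary set will consist of all subjects who are considered evaluable for the primary statistical analysis", and "This set will be used for the statistical analysis of the treatment comparisons defined in Section 16.3.1". The table in Section 10.0 instead assigns the primary analysis to the PK set. Appendices 4 and 5 do the same for the Part 2 statistical tables; in Appendix 5 this is the table titled "Statistical Analysis of OZ439 PK Parameters (Part 2)". Section 6.2 provides for replacements: "Replacement subjects will receive the number of the subject to be replaced, increased by 1000". For the comparisons within Part 2, Section 16.3.2 specifies: "The model will include fixed effects for treatment, period, and sequence, and a random effect for subject within sequence".

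**The concern.** Two neighbouring sentences use different numbers. The precision is worked out for 18 subjects, while the number the plan undertakes to secure is 15. Section 10.4 confines the treatment comparisons to evaluable subjects, so 15 could be the number analysed. Part 1 makes the contrast sharper, because there the same section ties its judgement of sufficiency to 8 enrolled with at least 6 evaluable.

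If the plan depended on reaching 1.75 to 2.28, it would have justified its size on a best case. The estimate of the cobicistat effect (Treatment D against Treatment C) would then be less precise than a reader expects. This is the only precision figure given for Part 2, so it deserves a check.

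**Working it through.** **Inputs.** From SAP Section 6.1: ratio 2.0, CV 23%, two-sided 90% interval, 18 randomised, at least 15 evaluable. From Section 16.3.2: log-transformed data and a model with treatment, period, sequence and random subject. Assumption: the CV is within-subject. The SAP does not label it, but this reading reproduces the printed interval.

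**Formula.** s = √ln(1 + 0.23²) = √ln(1.0529) = 0.2270. The interval is 2.0 × exp(±h), with h = t(0.95, df) × s × √(2/n).

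**The plan's own figure, n = 18.** The standard error is 0.2270 × √(2/18) = 0.0757. With df = n − 2 = 16, t = 1.746 and h = 0.132, which gives 1.752 to 2.283. With df = n − 1 = 17 it is 1.753 to 2.281. Both round to the printed 1.75 to 2.28, so there is no arithmetic error.

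**Fewer subjects.** The model in Section 16.3.2 uses all three periods. With complete data its residual df are (3n − 1) − (n − 1) − 2 − 2 = 2n − 4. The table shows both choices of df.

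| n | df = n − 2 | df = 2n − 4 (planned model) |
|---|---|---|
| 18 | 1.75 to 2.28 | 1.76 to 2.27 |
| 17 | 1.74 to 2.29 | 1.75 to 2.28 |
| 16 | 1.74 to 2.30 | 1.74 to 2.29 |
| 15 | 1.73 to 2.32 | 1.74 to 2.30 |

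At n = 15 the standard error is 0.2270 × √(2/15) = 0.0829. With df 13, t = 1.771 and h = 0.147. With df 26, t = 1.706 and h = 0.141.

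**Size of the difference.** Like for like, the log half-width at 15 exceeds that at 18 by 0.1468/0.1321 = 1.111, or 11%, with df n − 2. With df 2n − 4 it is 0.1414/0.1282 = 1.103, or 10%. Compared with the printed interval, the planned model at 15 lowers the lower limit by 0.01 and raises the upper limit by 0.02. At 17 it returns the printed interval.

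**Comparison with the uncertainty in the CV.** Keep n = 18 and df 16 and raise the CV from 23% to 25%: s = 0.2462, h = 0.143, interval 1.73 to 2.31. At a CV of 25.6% it is 1.73 to 2.32. A CV under 3 percentage points too low would therefore cost as much precision as losing three subjects.

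**Is there a contradiction in the text?** The interval is conditional on 18 subjects. The number 15 appears in a separate sentence as a minimum after losses, and no interval is attached to it. Both statements can be true together. Section 6.1 gives no maximum width, lower bound, margin or power that 15 subjects would have to meet.

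**The case for a change.** The strongest case for the concern is that a precision statement should describe the analysis the plan is sure to deliver. Section 10.4 makes evaluability a condition for the comparisons and requires Cmax and AUC0-inf under all three treatments, so losing a few subjects is realistic. Section 6.2 provides numbers for replacements but does not say when or how many. Every t-based interval at 15 is wider than the printed one. A single added sentence could give both intervals and label the CV as within-subject.

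Most of this is factually right. The interval at 15 is wider, by 10 to 11% on the log scale, and labelling the CV would spare the reader a back-calculation. What does not follow is that the plan is wrong. Giving precision at the planned number and then naming a minimum is coherent, and the judgement of sufficiency is not tied to any threshold that 15 subjects fail. The wider figure of 1.73 to 2.32 also rests on n − 2 degrees of freedom, whereas the planned three-period model has 2n − 4.

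It is also unsettled that only 15 would be analysed. Fifteen is a floor, replacements are provided for, and the table in Section 10.0 and the output lists assign the analysis to the broader PK set. That set admits a subject with a single estimable parameter. The mismatch between those places and Section 10.4 is a separate matter and does not make the precision figure wrong.

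**Conclusion.** The concern does not hold. The interval of 1.75 to 2.28 is correct for 18 subjects, a ratio of 2.0 and a CV of 23%, and the SAP claims it for nothing else. At the minimum of 15 the expected interval is 1.74 to 2.30 with the planned model's degrees of freedom, or 1.73 to 2.32 with n − 2. In an exploratory study with no target width or power, neither result undermines the judgement that the size is sufficient. Printing a second interval would alter no sample size, model, estimate or reported confidence interval, because the observed interval replaces the planning one.

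This conclusion assumes that the 23% is a within-subject CV, as the printed interval implies, and that analysed subjects contribute complete data in all three periods. It does not depend on which degrees of freedom are used.

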## 6.2 Randomization

Subjects who have met all eligibility criteria will receive a subject number upon inclusion in the study (for Part 1: subject numbers 101-108; for Part 2: subject numbers 201-218). They will receive the subject number according to the order of enrolment in Part 1 of the study, and according to the randomization code generated by the Biostatistics Department of PRA in Part 2 of the study. The subject number will ensure identification throughout the study. Replacement subjects will receive the number of the subject to be replaced, increased by 1000 (e.g. 1101 replacement number for subject number 101), and will be administered the same or remaining treatments in the same order.

In Part 2, subjects were randomized to 1 of 6 treatment sequences (BCD, BDC, CBD, CDB, DBC, or DCB), with 3 subjects per sequence (balanced randomization).

## 7.0 Overview of Planned Analysis

### 7.1 Changes from Protocol

In the protocol it was stated that a subject will be considered evaluable for the primary analysis if they have sufficient PK data to estimate all of the primary endpoints ( $C_{max}$ ,  $C_{168h}$ ,  $AUC_{0-168h}$ , and  $AUC_{0-inf}$ ) for the 3 treatments. This was changed in the SAP to: 'a subject will be considered evaluable for the primary analysis if they have sufficient PK data to estimate the primary endpoints  $C_{max}$  and  $AUC_{0-inf}$  for the 3 treatments'.

### 7.2 Interim Analysis and Key Results

Interim PK results of Part 1 will be provided to the Sponsor. The interim Tables, Figures and Listings (TFLs) will include a PK concentration table (Table 15.2.1), individual values and descriptive statistics of PK parameters (Table 15.2.2), a summary of the statistical analysis of bioavailability (Table 15.2.3), plots of combined individual PK profiles (Figure 15.2.6), and plots of geometric mean PK profiles (Figure 15.2.5).

### 7.3 Final Analysis

Draft TFLs will be provided with the draft CSR. After Sponsor comments have been incorporated, the TFLs will be finalized and incorporated in the final CSR.

## 8.0 Data Review

### 8.1 Data Management

Data handling and transfer will take place under the PRA Data Management Plan for the study.

### 8.2 Acceptance of Data for Summarization

Programming of analysis datasets and TFLs may be ongoing during the data management of the study. However, programming of analysis datasets and TFLs will be completed and quality controlled (QC'd) after database lock. Only quality assured (QA'd) results released by the Safety Laboratory, Bioanalytical Laboratory, or other external data source will be used for the programming of analysis datasets and TFLs for the final report. Any data values requiring investigation or corrections that are identified while programming the analysis datasets and TFLs will be sent to the project Data Manager. Database will not

be locked until the identified issues are resolved. If the issue affects the TFLs the Programmer or Statistician who identified the issue will follow it to resolution.

## 9.0 Definitions and General Analysis Methods

### 9.1 Analysis Data Presentation

#### 9.1.1 Rounding

In listings, data will be presented with the same precision as the original data. Derived data will be rounded for presentation purposes.

For all non-PK summaries, mean, Standard Deviation (SD), median, minimum and maximum will be presented with the same precision as the original data (i.e., the same number of decimals). The derived PK parameters, except  $t_{max}$ , will be listed and summarized with a precision of 3 significant digits or as integers when the value is  $>1000$ ;  $t_{max}$  values will be presented with 2 decimals, %AUC extra will be presented with 1 decimal.

CV% will be presented with 1 decimal and frequency percentages will be presented as whole numbers.

P-values will be reported to 4 decimal places; p-value less than 0.0001 will be reported as  $p < 0.0001$ .

#### 9.1.2 Imputation

Unless otherwise noted data will not be imputed. Exceptions are missing start and end times of AEs, see Section 17.1.1 and PK concentrations under lower limit of quantification (LLOQ), see Section 16.2.

#### 9.1.3 Descriptive Statistics

Unless otherwise indicated, continuous variables will be summarized with the following descriptive statistics: n (number of observations), (arithmetic) mean, SD, minimum (min) value, median, and maximum (max) value. For PK parameters the geometric mean (except for  $t_{max}$ ) and the coefficient of variation (CV%) will also be presented.

Categorical data will be summarized with frequencies and percentages. Percentages by categories will be based on the number of subjects exposed within a treatment.

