### 17.1.5 Electrocardiograms

ECG parameters will be listed and descriptive statistics of original values and change from baseline will be provided to summarize ECG parameters by treatment and scheduled time. At some time points triplicate 12-lead ECGs will be recorded. The average of these triplicate values will be used in the calculation of descriptive statistics and change from baseline, and the average of the triplicate values at pre-dose will be used as baseline. The individual triplicate values will be listed.

A frequency table of QTc (Bazett and Fridericia) values will be presented by treatment and scheduled time. The number of incidences (number of subjects) and percentage of subjects will be presented. The following categories will be used:

- < 450 ms
- $\geq$  450 - 480 ms
- $\geq$  480 - 500 ms
- $\geq$  500 ms

A frequency table of QTc (Bazett and Fridericia) change from baseline values will be presented by treatment and scheduled time. The number of incidences (number of subjects) and percentage of subjects will be presented. The following categories will be used:

- < 30 ms
- $\geq$  30 - 60 ms
- $\geq$  60 ms

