### Appendix 3: Schedule of Assessments – Part 2

Study Day	Screening -28 to -2	Assessment Period 1, 2 or 3 																				Follow-up 15-19 of Period 3
		Pre-Treatment -1	Treatment 0	1	2	3	4	5	6	8	12	16	24	48	72	96	168	216	264	312		
Hours		Pre-dose	0	0.5	1	2	3	4	5	6	8	12	16	24	48	72	96	168	216	264	312	
Confinement		X	X	X	X	X	X	X	X	X	X	X	X	X								
Ambulatory visit															X	X	X	X	X	X	X	X
Admission		X																				
Discharge														X								
Informed consent	X																					
Medical history	X																					
Demographics	X																					
Prior and concomitant medication check	X	X	X	X	X	X	X	X	X	X	X	X	X	X	X	X	X	X	X	X	X	X
Body weight and height (including BMI calculation)	X																					
Physical examination	X	X 3	X 											X 3								X a
Serology (HBsAg, anti-HCV, anti-HIV 1 and 2)	X																					
Drug and alcohol screen	X	X																				
Pregnancy test (females only)	X	X 4																				
FSH (females only)	X																					
Clinical laboratory 	X 	X 5				X								X			X		X			X
12-lead ECG 	X	X	X			X		X			X	X		X			X		X			X
Vital signs 	X	X	X			X		X			X	X		X			X		X			X
Eligibility check	X	X	X																			
Drug administration				X																		
PK blood samples for OZ439			X		X	X	X	X	X	X	X	X	X	X	X	X	X	X	X	X	X	X
PK blood samples for cobicistat 			X		X	X	X	X	X	X	X	X	X	X	X	X						
Blood samples for OZ439 metabolites 								X			X	X		X								
Adverse events	X	X	X	X	X	X	X	X	X	X	X	X	X	X	X	X	X	X	X	X	X	X

- 1 Subjects will be in the clinic for 3 periods, each period from Day -1 until 24 hours post-dose (Day 2). Subjects will return for ambulatory visits on Days 3, 4, 5 and 8 (at 48, 72, 96 and 168 hours post-dose) of each period
- 2 Additional ambulatory visits on Days 10, 12 and 14 for Treatment D only (a single oral dose of 400 mg OZ439 simple granules administered as a 60-mL dispersion and co-administered with a 150 mg cobicistat tablet [CYP3A4 inhibitor]). Day 14 will coincide with Day -1 of the next period when a subject is randomized to Treatment D in Period 1 or Period 2.
- 3 A targeted physical examination of applicable body systems will be performed if needed as per the judgment of the PI (eg, if the subject reports AEs) at pre-dose, on Day -1 and at discharge

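### The QTc frequency tables take all subjects exposed to a treatment as denominator; if the single Part 2 follow-up ECG is tabulated under the Period 3 treatment, percentages in that row come out three times too low

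*SAP*

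**What the plan says.** Section 9.1.3 of the SAP gives the general rule for categorical data: "Percentages by categories will be based on the number of subjects exposed within a treatment". The qualifier about other indications in that section opens the sentence on continuous variables, not this one. For continuous variables the same section reports n as the number of observations.

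Section 17.1.5 then defines two QTc tables: "A frequency table of QTc (Bazett and Fridericia) values will be presented by treatment and scheduled time", and "A frequency table of QTc (Bazett and Fridericia) change from baseline values will be presented by treatment and scheduled time". For both, "The number of incidences (number of subjects) and percentage of subjects will be presented". Neither table is given its own denominator, and Section 9.5 says that no table shells will be supplied.

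On the design, Section 6.0 states for Part 2 that "each subject will receive a single dose of each of the following 3 treatments in a randomized order". Section 6.2 lists six sequences (BCD, BDC, CBD, CDB, DBC, DCB) with three subjects in each. The Part 2 schedule in Appendix 3 has a single follow-up column, headed "Follow-up 15-19 of Period 3", and the 12-lead ECG row is marked in it.

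**The concern.** Exposure is a natural denominator for adverse-event incidence, where every exposed subject is under observation. It fits a table split by time point only if every exposed subject is due a measurement at that time. The Part 2 follow-up visit takes place once per subject, while exposure is counted once per subject and treatment. The row can therefore have a denominator well above the number of subjects who could have been measured, even if no subject drops out and no ECG is missed.

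What is at stake is how one row of two descriptive safety tables reads. A low percentage in a high QTc category at follow-up would partly reflect the number of subjects without a follow-up ECG under that treatment. The row would also disagree with the continuous ECG summary of the same data, which would show n = 6.

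**Working it through.** **Inputs**
- Denominator: subjects exposed to the treatment (Section 9.1.3).
- Layout: treatment by scheduled time (Section 17.1.5).
- Sequences: six, three subjects each (Section 6.2).
- Follow-up: one visit, Day 15-19 of Period 3, with an ECG (Appendix 3).
- Percentages shown as whole numbers (Section 9.1.1).
- Assumption, not stated in the SAP: the follow-up ECG is tabulated under the treatment given in Period 3.

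**Step 1: reproduce the Part 2 sample size.** 6 sequences × 3 subjects = 18, as stated in Sections 6.0 and 6.1.

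**Step 2: exposed subjects per treatment.** Each of B, C and D appears in all six sequences, so 6 × 3 = 18 subjects are exposed to each treatment if all complete.

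**Step 3: subjects with a follow-up ECG under each treatment.** Count the sequences that end in that treatment.

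| Treatment | Sequences ending in it | Subjects with follow-up | Exposed | Exposed / followed up |
|---|---|---|---|---|
| B | CDB, DCB | 2 × 3 = 6 | 18 | 3.0 |
| C | BDC, DBC | 2 × 3 = 6 | 18 | 3.0 |
| D | BCD, CBD | 2 × 3 = 6 | 18 | 3.0 |

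**Step 4: effect on the printed percentage at follow-up.**

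| Subjects in category | Rule as written (k/18) | Among those measured (k/6) |
|---|---|---|
| 1 | 6% | 17% |
| 2 | 11% | 33% |
| 3 | 17% | 50% |
| 6 | 33% | 100% |

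Six subjects at most can be classified, so before rounding the categories of the row sum to 6/18 = 33%.

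**Step 5: range with dropout.** Section 6.1 plans that "18 subjects will be randomized to ensure data in 15 evaluable subjects for the PK endpoints". Taking 15 to 18 exposed and, as an assumption, 4 to 6 followed up per treatment, the factor runs from 15/6 = 2.5 to 18/4 = 4.5.

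**Step 6: other rows.** In-period ECGs are scheduled for every subject on the treatment, and the additional late visits are for Treatment D only, so exposed and scheduled numbers agree. One missing ECG among 18 changes 1/17 = 5.9% to 1/18 = 5.6%, and both print as 6%. Part 1 has one treatment and one follow-up visit, so it has no structural mismatch.

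**Step 7: the alternative layout.** If the follow-up ECG were shown once, pooled over treatments, 18 treated subjects would face 18 scheduled ECGs, and the factor would be 1.

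**The case against.** The strongest objection is that the threefold figure needs a premise that the SAP does not state. Only adverse events have a rule assigning post-dose observations to a period (Section 17.1.1). Baseline and study day are defined per period (Sections 9.2.1 and 9.2.3), but nothing assigns the end-of-study ECG to a treatment. This stands: the figure is conditional. Tabulation under the Period 3 treatment remains the natural reading, because the visit is numbered within Period 3, baseline is per period, summaries are by treatment (Section 9.1.4), and no pooled column is provided for.

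A second objection is that nothing is concealed. The tables must also give the number of subjects, ECG parameters are listed, and the continuous ECG summary reports n. A subject at or above 500 ms appears as a count of 1 under either denominator. This also stands, and with 18 subjects the count carries most of the information.

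A third is that a percentage of exposed subjects is a defined quantity and a row summing to 33% would reveal itself. That is partly fair. The rule does not classify unmeasured subjects as normal, and Section 9.1.2 says data are not imputed unless noted. But a reader who looks at a single category percentage would not see the gap, and would naturally take it as a rate among subjects measured at that visit.

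A reader might infer more than this: that the QTc outlier display as a whole is distorted, or that cases are hidden. The SAP does not support either reading. The structural mismatch is confined to the Part 2 follow-up row.

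**Conclusion.** The point holds in a limited, conditional form. The general denominator in Section 9.1.3 does not suit categorical tables by time point, and Section 17.1.5 does not replace it. If the Part 2 follow-up ECG is tabulated under the Period 3 treatment, that row's percentages are one third of the rate among subjects measured. The factor is exactly 3.0 with full completion and 2.5 to 4.5 under the assumed dropout range.

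It would be wrong to state the threefold understatement as a certain consequence of the SAP, since the assignment of that ECG is left open. The tables are descriptive, the SAP calls the study exploratory, and no test or decision in it rests on a QTc percentage. PK conclusions are untouched. This is a minor correction, worth making because the rule as written leads to a misleading number at a planned visit even when the data are complete.

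**What to change.** In Section 9.1.3 or 17.1.5, make three statements:

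1. For categorical tables by scheduled time, the denominator is the number of subjects in that treatment with a non-missing value at that time point. For change from baseline, both the baseline and the post-dose value must be present. The table shows this n.
2. The Part 2 follow-up ECG is assigned either to the treatment given in Period 3 or to a single row pooled over treatments.
3. The number exposed remains the denominator for adverse-event incidence.

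The cost is a few lines of SAP text and a changed denominator in Tables 15.3.4.3 and 15.3.4.4. No new data or analysis are needed, and the tables would then agree with the observation-based n already used for continuous ECG summaries.
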